3.2 SECONDARY OBJECTIVES

1. Describe the effect of 12 weeks of treatment of GTx-024 on the frequency of voids/day as assessed by the 3 day voiding diary.
2. Describe the effect of 12 weeks of treatment of GTx-024 on urine volume per void as assessed by the 3 day voiding diary.

3. Describe the effect of 12 weeks of treatment of GTx-024 on SUI as assessed by 24 hour pad weight test.
4. Describe the effect of 12 weeks of treatment of GTx-024 on SUI as assessed by the Urethral Pressure Profile (UPP).
5. Describe the effect of 12 weeks of treatment of GTx-024 on SUI as assessed by the Bladder Stress Test.
6. Describe the effect of 12 weeks of treatment of GTx-024 on patient reported stress urinary incontinence symptoms as assessed by the MESA Urinary Questionnaire.
7. Describe the effect of 12 weeks of treatment of GTx-024 on patient reported impression of symptom severity as assessed by the Patient Global Impression of Severity Scale (PGI-S).
8. Describe the effect of 12 weeks of treatment of GTx-024 on patient reported impression of improvement as assessed by the Patient Global Impression of Improvement Scale (PGI-I).
9. Describe the effect of 12 weeks of treatment of GTx-024 on patient reported urogenital distress as assessed by the Urinary Distress Inventory Questionnaire (UDI-6).
10. Describe the effect of 12 weeks of treatment of GTx-024 on patient reported impact of urinary incontinence on daily life as assessed by the Incontinence Impact Questionnaire (IIQ-7).
11. Describe the effect of 12 weeks of treatment of GTx-024 on patient reported sexual function as assessed by the Female Sexual Function Index Questionnaire (FSFI).
12. Describe the effect of 12 weeks of treatment of GTx-024 on pelvic floor muscles as measured by MRI.

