3.3 STUDY END POINTS

Primary end point

1. Change in frequency of daily stress urinary incontinence episodes from Baseline to Week 12.

Secondary end points

1. Change in frequency of daily voids from Baseline to Week 12.
2. Change in urine volume per void from Baseline to Week 12.
3. Change in 24 hour pad weight from Baseline to Week 12.
4. Change in maximum urethral closure pressure measurements from Baseline to Week 12.
5. Change in urine leakage (yes/no) on the Bladder Stress Test from Baseline to Week 12 as assessed while (a) coughing, and/or (b) performing a Valsalva maneuver.
6. Change in total score on the stress incontinence section of the MESA Urinary Questionnaire from Baseline to Week 12.
7. Change in Patient Global Impression of Severity (PGI-S) Scale from Baseline to Week 12.
8. Patient Global Impression of Improvement (PGI-I) Scale at Week 12.
9. Change in total score on the Urinary Distress Inventory (UDI-6) from Baseline to Week 12.
10. Change in total score on the Incontinence Impact Questionnaire (IIQ-7) from Baseline to Week 12.
11. Change in total score on the Female Sexual Function Index (FSFI) from Baseline to Week 12 as well as the change in subdomain scores: libido, arousal, lubrication, orgasm, satisfaction, and pain.
12. Change in pelvic floor muscles from Baseline to Week 12 as measured by MRI. Quantitative assessments may include the area of the levator hiatus, the anteroposterior and transverse diameters, and other relevant parameters.

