Mammography is the process of using low-energy X-rays to examine the human breast, which is used as a diagnostic and screening tool. The goal of mammography is the early detection of breast cancer, typically through detection of characteristic masses and/or microcalcifications.

Magnetic Resonance Imaging(MRI)

MRI will be done at baseline and end of treatment to observe changes in pelvic floor muscles along with the thickness of the endometrium (mm). Quantitative assessments may include the area of the levator, the anteroposterior and transverse diameters, and/or other relevant parameters. Endometrial thickness can accurately be assessed by MRI (Stanislavsky, Weerakkody, et al., 2015; Nakamura et al., 2014); therefore, it is being used as a safety assessment in this study.

Medical, Epidemiological and Social Aspects of Aging (MESA) Questionnaire

The MESA questionnaire measures severity of specific types (stress, urgency, mixed) of urinary incontinence (UI). Two subscales, the urgency UI (6 items) and the stress UI (9 items). Test-retest reliability on “any incontinence” is high (agreement coefficient = .89). Validity (agreement between self-report on the MESA and clinician’s assessment) = 87% in women. The MESA questionnaire has demonstrated agreement on incontinence = 79% and 69% and 72% accuracy in predicting urodynamic diagnosis of stress UI and uninhibited detrusor contraction (Herzog, 1990a; Herzog, 1990b).

3 Day Voiding Diary

Subjects will record each episode of urinary leakage and record its severity. Subjects will also be asked to record urinary frequency, and urgency. Urine volume will also be recorded. 3 day bladder diaries are reliable measures of mean number of UI episodes/day, UI type, mean voids/24 hours, and mean voids during sleeping hours. 2-week test-retest results correlate with diurnal micturition ($r=.89$, $p<0.001$) and UI episodes ($r=.91$, $p<0.001$). Compared to participant recall of the previous week, Spearman rank correlation = .57 for voiding frequency and .70 for UI episodes (Brown, 2003; Locher, 2001; Wyman, 1988). For this study, any episode of vaginal discharge or spotting will also be recorded on the diary.

Patient Global Impression of Improvement (PGI-I)

PGI-I is a global rating of improvement using 7-point scale. Construct validity was established in two randomized controlled studies ($n=1,133$ subjects) of drug treatment for predominant stress incontinence (Wagner, 1996; Yalcin, 2003).

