10. STATISTICAL CONSIDERATIONS

Since this is a proof of concept feasibility study, no power calculation is needed. Based on Dalton, 2011, 10-20% of patients may withdraw from the study before completing treatment. Therefore, we will recruit up to 35 patients meeting inclusion/exclusion criteria until 30 subjects have completed treatment. Descriptive statistics will be used to explore changes in primary and secondary outcomes measures between baseline and end of treatment. Although the primary efficacy measure will be a change in frequency of daily stress leaks between Baseline and Week 14 weeks, response to treatment will also consider secondary efficacy measures (change in frequency of voids per day, urine volume per void, change in 24 hour pad weight, responses to validated questionnaires, changes in UPP measures, changes in sexual function), and change in pelvic floor muscles as measured by MRI. Safety will be reported by the number and type of adverse events reported during treatment. No imputations for missing data will be conducted. There will be no adjustment for multiple testing.

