- Change in Patient Global Impression of Severity (PGI-S) Scale from Baseline to Week 12 will be computed and this change will be summarized with descriptive statistics (min, max, median, mean, standard deviation) and analyzed for a significant change from Baseline using the Exact Wilcoxon sign rank test.
- Patient Global Impression of Improvement (PGI-I) Scale at Week 12. Descriptive statistics, (min, max, median, mean, standard deviation) will summarize these scores.
- Change in total score on the Urinary Distress Inventory (UDI-6) from Baseline to Week 12 will be computed and this change will be summarized with descriptive statistics (min, max, median, mean, standard deviation) and analyzed for a significant change from Baseline using the Exact Wilcoxon sign rank test.
- Change in total score on the Incontinence Impact Questionnaire (IIQ-7) from Baseline to Week 12 will be computed and this change will be summarized with descriptive statistics (min, max, median, mean, standard deviation) and analyzed for a significant change from Baseline using the Exact Wilcoxon sign rank test.
- Change in total score on the Female Sexual Function Index (FSFI) as well as the change in subdomain scores: libido, arousal, lubrication, orgasm, satisfaction, and pain from Baseline to Week 12 will be computed and these changes will be summarized with descriptive statistics (min, max, median, mean, standard deviation) and analyzed for a significant change from Baseline using the Exact Wilcoxon sign rank test.

- Changes in pelvic floor muscles from Baseline to Week 12 will be summarized with descriptive statistics (min, max, median, mean, standard deviation) and analyzed for a significant change from Baseline using the Exact Wilcoxon sign rank test.
- Qualitative changes in pelvic muscles will be described as decreased, increased or no change at Week 12 relative to Baseline.

Exploratory Analyses

Changes from baseline to each of the assessment times prior to Week 12 for the above endpoints will be explored, described and tested for significance using the same analytical methods noted for the primary and secondary objectives above. Durability treatment will be assessed by evaluating changes in study measures between week 12 and 16 (end of study). There will be no adjustment for multiple testing, nor will any data be imputed.

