2/27 = 7%	6/27 = 22%	10/27 = 37%	14/27 = 52%	18/27 = 67%	22/27 = 81%	26/27 = 96%
3/27 = 11%	7/27 = 26%	11/27 = 41%	15/27 = 56%	19/27 = 70%	23/27 = 85%	27/27 = 100%
4/27 = 15%	8/27 = 30%	12/27 = 44%	16/27 = 59%	20/27 = 74%	24/27 = 89%	

Total Score _____/27

2. APPENDIX B: PATIENT GLOBAL IMPRESSION OF SEVERITY (PGI-S) SCALE AND PATIENT GLOBAL IMPRESSION OF IMPROVEMENT (PGI-I) SCALE

Patient Global Impression of Severity (PGI-S) Scale

Check the one number that best describes how your urinary tract condition is now.

1. Normal
2. Mild
3. Moderate
4. Severe

Patient Global Impression of Improvement (PGI-I) Scale

Check the one number that best describes how your urinary tract condition is now, compared with how it was before you began taking medication in this study.

1. Very much better
2. Much better
3. A little better
4. No change
5. A little worse
6. Much worse
7. Very much worse

3. APPENDIX C: URINARY DISTRESS INVENTORY (UDI-6) AND INCONTINENCE IMPACT QUESTIONNAIRE (IIQ-7)

Urinary Distress Inventory (UDI-6)

1. Do you experience, and, if so, how much are you bothered by frequent urination?

Not at all **0** *Slightly* **1** *Moderately* **3** *Greatly***4**

2. Do you experience, and, if so, how much are you bothered by urine leakage related to the feeling of urgency?

Not at all **0** *Slightly* **1** *Moderately* **3** *Greatly***4**

3. Do you experience, and, if so, how much are you bothered by urine leakage related to physical activity, coughing, or sneezing?

Not at all **0** *Slightly* **1** *Moderately* **3** *Greatly***4**

4. Do you experience, and, if so, how much are you bothered by small amounts of urine leakage (drops)?

Not at all **0** *Slightly* **1** *Moderately* **3** *Greatly***4**

5. Do you experience, and, if so, how much are you bothered by difficulty emptying your bladder?

Not at all **0** *Slightly* **1** *Moderately* **3** *Greatly***4**

6. Do you experience, and, if so, how much are you bothered by pain or discomfort in the lower abdominal or genital area?

Not at all **0** *Slightly* **1** *Moderately* **3** *Greatly***4**

Incontinence Impact Questionnaire (IIQ-7)

7. Has urine leakage affected your ability to do household chores (cooking, cleaning, laundry, etc)?

Not at all **0** *Slightly* **1** *Moderately* **3** *Greatly***4**

8. Has urine leakage affected your physical recreation such as walking, swimming, or other exercise?

Not at all **0** *Slightly* **1** *Moderately* **3** *Greatly***4**

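### The planned PGI-I summary (min, max, median, mean, SD) does not in general fix how many women rated themselves better; category counts and one proportion with an exact interval would

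*Combined protocol and SAP*

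**What the plan says.** Section 3.2 (secondary objective 8) is to describe the effect of 12 weeks of treatment on the patient's impression of improvement. Section 3.3 (secondary end point 8) takes the Week 12 rating itself as the endpoint, not a change score. Section 8 describes the instrument: "PGI-I is a global rating of improvement using 7-point scale". Appendix B asks each woman to rate "how your urinary tract condition is now, compared with how it was before you began taking medication in this study". The answers run from 1 (very much better) to 7 (very much worse). The last category that means improvement is "3. A little better", and category 4 is no change.

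The whole analysis in Section 10.1 is: "Patient Global Impression of Improvement (PGI-I) Scale at Week 12. Descriptive statistics, (min, max, median, mean, standard deviation) will summarize these scores". The other scored questionnaires there (MESA stress section, PGI-S, UDI-6, IIQ-7, FSFI) get the same five statistics plus an exact Wilcoxon test of change from baseline.

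Nothing else in the document adds PGI-I counts:

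- The exploratory analyses reuse the same methods for changes from baseline at earlier visits. Table 1 first schedules PGI-I at Week 4, so it has no baseline value.
- The mixed models estimate a slope over time.
- Category reporting (decreased, increased, no change) is planned only for qualitative pelvic muscle findings.

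**The concern.** PGI-I is the one endpoint that asks women directly whether they are better than before treatment. The natural description of such a rating is how many women chose each answer, and how many chose one that means better. A mean and SD of the category numbers treat the labels as equally spaced measurements. The median respects the ordering but gives only one point of the distribution.

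At stake is how much a reader learns from this endpoint. Section 10 says that questionnaire responses will also be considered when response to treatment is judged, and Section 10.1 looks ahead to planning future trials. A proportion improved, with its precision, serves both purposes better than a mean category number. If the proportion is added only at reporting, its cut-off will be chosen after the ratings have been seen.

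**Working it through.** The plan states no figure for this endpoint, so there is none to reproduce. The question is whether the five planned statistics determine the number of women in categories 1 to 3.

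**Inputs**

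- Seven categories, with 1 to 3 meaning better: Appendix B labels.
- Statistics reported: min, max, median, mean, SD (Section 10.1).
- n = 30, from Section 10: "we will recruit up to 35 patients meeting inclusion/exclusion criteria until 30 subjects have completed treatment". This is an assumption about the number rated at Week 12.
- The distributions are hypothetical. The documents give no expected PGI-I distribution.

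**What the median alone gives.** With n = 30 the median is the average of the 15th and 16th ordered ratings. If it is 3 or less, the 15th rating is 3 or less, so at least 15 women improved. If it is above 3, the 16th rating is above 3, so at most 15 improved. A maximum of 3 or less would mean that all improved.

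**Two sets with the same planned summary**

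| | Set 1 | Set 2 |
|---|---|---|
| Counts, categories 1 to 7 | 4,0,0,18,8,0,0 | 1,2,12,0,15,0,0 |
| Sum | 4 + 72 + 40 = 116 | 1 + 4 + 36 + 75 = 116 |
| Sum of squares | 4 + 288 + 200 = 492 | 1 + 8 + 108 + 375 = 492 |
| Min, max | 1, 5 | 1, 5 |
| 15th and 16th ratings | 4 and 4 | 3 and 5 |
| Median | 4 | 4 |
| Improved (categories 1 to 3) | 4/30 = 13% | 15/30 = 50% |
| Exact 95% interval | 3.8% to 30.7% | 31.3% to 68.7% |

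Both means are 116/30 = 3.87. Both SDs are √[(492 − 116²/30)/29] = √(43.467/29) = 1.224. In Set 1, 18 of 30 women report no change. In Set 2 none do: half are better and half a little worse. The difference is 11 women, or 11/30 = 37 percentage points.

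**A pair with median 3.** Counts (1,14,0,14,1,0,0) and (3,4,18,0,5,0,0) both have sum 90, sum of squares 306, min 1, max 5, median 3, mean 3.00 and SD √[(306 − 270)/29] = 1.114. Improved: 15/30 (50%; exact 95% interval 31.3% to 68.7%) against 25/30 (83%; 65.3% to 94.4%).

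**All cases.** The 1,947,792 ways to place 30 women in seven categories give 123,757 distinct summaries. About 31% of these fix the number improved. Within one summary the number can differ by up to 12 women (12/30 = 40 percentage points). The 31% counts possible summaries and is not a probability. The match was on exact sums, so rounding the reported mean and SD could only add ambiguity.

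**The case against.** Nothing stated is wrong. The objective is to describe, the study is a proof of concept, and a median with range, mean and SD is a description. The median suits an ordinal scale and tells the reader whether at least, or at most, half the women improved. The pairs above were selected to show a wide gap, and nothing in the documents suggests that real ratings will look like them. No responder cut-off is defined anywhere. The ratings are collected and the questionnaires are kept as source documents (Section 13.1.1), so a frequency table can be produced at any time.

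Most of this stands, and it limits the point. Three stronger readings are tempting, and the documents do not support them:

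- A reader might infer that the plan fails secondary objective 8. It describes that endpoint incompletely; it does not leave it undescribed.
- A reader might infer that only moments and a range are reported. The median is planned, and it bounds the count.
- A reader might infer that one summary can hide contradictory trial results. The median prevents a clear majority improved and a clear minority improved from sharing a summary. What stays hidden is how large the share is on one side of one half.

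The missing test is also understandable, because the Wilcoxon test in Section 10.1 is of change from baseline and PGI-I has no baseline value.

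What the objection does not remove is that the number improved is usually not recoverable from the planned output, while counts on the same data would give it exactly.

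**Conclusion.** The point holds as a minor improvement that costs almost nothing. For n = 30, one planned summary is compatible with 4/30 or 15/30 women improved, and across all distributions the ambiguity reaches 12 women. This rests on taking categories 1 to 3 as improved, which follows the Appendix B labels, and on 30 rated women. The examples show what the summary cannot separate; they do not predict the data.

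The gap is in planned reporting for one secondary endpoint, not in data collection. The primary endpoint is unaffected. A proportion improved should not be read as a drug effect: the study is single-arm and open-label, and Section 2.1 itself cites falls in incontinence episodes of 41% and 27% on placebo in duloxetine trials.

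**What to change.** In Section 10.1, replace the PGI-I line with wording such as: *PGI-I at Week 12 will be summarised as the number and percentage of women in each of the seven categories, with the median. The number and percentage better to any degree (categories 1 to 3) will be given with an exact (Clopper-Pearson) 95% confidence interval. Percentages use women with a Week 12 rating; women without one are shown in a separate row.*

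The missing row fits the plan's rule of no imputation and its expectation that 10 to 20% may withdraw (Section 10). A percentage much or very much better (categories 1 and 2) is an optional addition. If it is wanted, name it before the ratings are seen, because the documents define no responder cut-off. The mean and SD may stay, but are not needed.

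The cost is one line of text and one table, with no new data, visits or procedures.

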1 PROTOCOL SUMMARY

Title:	GTx-024 as a Treatment for Stress Urinary Incontinence in Women: A Proof of Concept Study
Sponsor:	GTx, Inc.
Indication:	Stress Urinary Incontinence (SUI)
Study Design:	This is a single site, single-arm, open-label proof of concept feasibility study.
Objectives:	
Primary Objective Describe the effect of 12 weeks of treatment of GTx-024 on the number of stress incontinence episodes/day as assessed by the 3 day voiding diary.
 
Secondary Objectives Describe the effect of 12 weeks of treatment of GTx-024 on the number of voids/day as assessed by the 3 day voiding diary.
 
Describe the effect of 12 weeks of treatment of GTx-024 on urine volume per void as assessed by the 3 day voiding diary.
 
Describe the effect of 12 weeks of treatment of GTx-024 on SUI as assessed by 24 hour pad weight test.
 
Describe the effect of 12 weeks of treatment of GTx-024 on SUI as assessed by the Urethral Pressure Profile (UPP).
 
Describe the effect of 12 weeks of treatment of GTx-024 on SUI as assessed by the Bladder Stress Test.
 
Describe the effect of 12 weeks of treatment of GTx-024 on patient reported stress urinary incontinence symptoms as assessed by the MESA Urinary Questionnaire.
 
Describe the effect of 12 weeks of treatment of GTx-024 on patient reported impression of stress urinary incontinence severity as assessed by the Patient Global Impression of Severity Scale (PGI-S)
 
Describe the effect of 12 weeks of treatment of GTx-024 on patient reported impression of improvement as assessed by the Patient Global Impression of Improvement Scale (PGI-I).
 
Describe the effect of 12 weeks of treatment of GTx-024 on patient reported urogenital distress as assessed by the Urinary Distress Inventory Questionnaire (UDI-6).

	
Describe the effect of 12 weeks of treatment of GTx-024 on patient reported impact of urinary incontinence on daily life as assessed by the Incontinence Impact Questionnaire (IIQ-7).
 
Describe the effect of 12 weeks of treatment of GTx-024 on patient reported sexual function as indicated on the completion of the Female Sexual Function Index Questionnaire (FSFI).
 
Describe the effect of 12 weeks of treatment of GTx-024 on pelvic floor muscles as measured by MRI.
 
Safety objective: To describe the safety profile of GTx-024 3 mg PO daily in subjects with SUI.

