¹ Age 18 to 80 years old is clinically confirmed as postmenopausal. Subjects must have undergone the onset of spontaneous, medically induced or surgical menopause prior to the start of this study. Postmenopausal is defined as 12 months of spontaneous amenorrhea or 6 months of spontaneous amenorrhea with serum FSH levels > 40 mIU/ml or 6 weeks postsurgical bilateral oophorectomy with or without hysterectomy.

² Mammogram within the last 6 months conducted outside the protocol may be utilized. Provided the data is available for assessment in this protocol, an additional mammogram will not be required.

³ Visit 1, Baseline, may not be completed until all results of screening tests have been evaluated.

⁴ After confirmation of meeting all eligibility criteria.

ROLES AND RESPONSIBILITIES

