Extensive clinical data related to the use of GTx-024 are described below; however, there are both pre-clinical and clinical data supporting the specific investigation of GTx-024 for the treatment of SUI. Among the preclinical findings are that GTx-024 has androgenic and anabolic activity in male and female rat models (Preclinical Reports n030105GTx024 and n112012.1). GTx-024 has consistently been observed to increase body weight, specifically muscle, in female rats. In a male rat model, with castrate levels of serum testosterone (similar to what might be expected in females), GTx-024 has the ability to induce hypertrophy of the levator ani muscle to approximately 120% of an intact male. These studies together provide an approximation of the expected effect of GTx-024, since currently there are no data in female models regarding levator ani hypertrophy or stress urinary incontinence (Preclinical Report n112012.1). In two phase 3 studies (G300504 and G300505), 3 mg daily GTx-024 results in a mild increase (approximately 1.7%) in lean body mass with no differential effect in males and females. Based upon these preclinical and clinical analyses, we anticipate significant growth/bulking of the levator ani in females with SUI, which may also result in improvements in associated symptoms, and are therefore the focus of the study outlined herein.

Ongoing and Completed Clinical Trials with GTx-024

The following Phase 1, 2, and 3 clinical trials have been completed or are ongoing with GTx-024.

1. Protocol G100401, a Phase 1 single ascending dose study in 96 healthy, young, male volunteers;
2. Protocol G100402, a Phase 1 multiple ascending dose study in 50 healthy, young, male volunteers, and 23 elderly male volunteers with truncal obesity;
3. Protocol G100503, a Phase 1 single dose pharmacokinetic study to assess the effect of a dosage regimen that simulates a sustained release formulation to an immediate release formulation in 18 healthy, young male volunteers and 18 postmenopausal women;
4. Protocol G100506, a Phase 1 single dose pharmacokinetic study to assess the relative bioavailability of a 3 mg hard shell capsule formulation to be used during continued clinical development and to assess the effect of food on the pharmacokinetics of the 3 mg softgel formulation in 27 healthy, young, male volunteers;
5. Protocol 006, a Phase 1 single dose and multiple dose pharmacokinetic study in 24 postmenopausal, Japanese women;

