5.2 SUBJECT EXCLUSION CRITERIA

Subject Exclusion Criteria: Subjects eligible for this study must not meet any of the following criteria:

1. Pelvic floor physical therapy within the last 6 months
2. History of pelvic radiation treatment
3. History of urethral diverticula
4. History of urethral sling, anterior prolapse repair, ureteral bulking agents and/or other SUI procedure or surgery
5. Known vesicoureteral reflux, vaginal prolapse beyond the introitus, or other significant pelvic floor abnormalities
6. Patient has urinary incontinence of neurogenic etiology
7. Patient is morbidly obese (defined as 100 pounds over their ideal body weight, or body mass index 40 or greater)
8. Chronic hepatitis
9. Hepatic cirrhosis
10. HIV and/or hepatitis A, B, or C

11. Subjects taking systemic hormone products (excludes intravaginal application of estradiol topical/tablet agents and hormones delivered via vaginal rings)
12. Subjects with a history of breast or endometrial cancer.
13. Subjects with cerebrovascular disease, thromboembolic disorders, myocardial infarction, or angina.
14. Subject with an entry measurement of > 5 mm endometrial stripe thickness as measured by MRI.
15. Any other condition which per investigators' judgement may increase subject risk
16. Clinically confirmed urinary tract infection

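### The plan does not require the pelvic-floor MRI scans to be read masked to scan order, and the three-category change call has no cut-off

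*Combined protocol and SAP*

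**What the plan says.** **Design.** The Protocol Summary states: "This is a single site, single-arm, open-label proof of concept feasibility study". Every subject who completes takes the drug between the two scans, so the visit label by itself identifies the post-treatment scan.

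**Procedure (Section 8).** "MRI will be done at baseline and end of treatment to observe changes in pelvic floor muscles along with the thickness of the endometrium (mm"). The paragraph goes on to possible measurements and to the use of endometrial thickness for safety. It does not name a reader, a number of readers, a reading sequence or any masking.

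**Endpoint (Section 3.3, secondary endpoint 12).** "Quantitative assessments may include the area of the levator hiatus, the anteroposterior and transverse diameters, and other relevant parameters".

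**Analysis (Section 10.1).** There are two MRI items. The first is quantitative: "Changes in pelvic floor muscles from Baseline to Week 12 will be summarized with descriptive statistics (min, max, median, mean, standard deviation"), followed by the exact Wilcoxon signed-rank test. The second has no test attached: "Qualitative changes in pelvic muscles will be described as decreased, increased or no change at Week 12 relative to Baseline".

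**Expectation and use.** Section 2.1 says "we anticipate significant growth/bulking of the levator ani in females with SUI". The opening paragraph of Section 10 lists MRI change among the measures considered in judging response, and rules out adjustment for multiple testing.

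**Reads with fixed timing.** Exclusion criterion 14 in Section 5.2 is "Subject with an entry measurement of > 5 mm endometrial stripe thickness as measured by MRI", and a footnote to Table 1 says "Visit 1, Baseline, may not be completed until all results of screening tests have been evaluated". The baseline endometrial read therefore has to be done before dosing.

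**The concern.** Section 2.1 argues that MRI adds a quantitative view of the pelvic floor beyond what symptoms show. That added value depends on the read not being steered by what the reader expects. Diaries and questionnaires in an open-label study cannot be shielded in this way. Stored images can, because the labels can be removed before reading. If the plan does not ask for this, someone who knows which scan came after treatment, in a study that anticipates muscle growth, may place contours or call categories in the expected direction. With one arm, nothing subtracts such a shift, and it would look like a drug effect.

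**Working it through.** **1. Is there a figure in the plan to reproduce?** No. Section 10 says no power calculation is needed, and no effect size, SD, alpha or measurement error is given for MRI. The only number used below is the target of 30 completers.

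**2. Which elements of the read are specified?**

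| Element | Section 8 | Section 3.3 | Section 10.1 |
|---|---|---|---|
| When scans are taken | Baseline, end of treatment | Baseline, Week 12 | Baseline, Week 12 |
| What is measured | Examples, list left open | Examples, list left open | Pelvic floor muscles, not itemised |
| Reader or number of readers | Not stated | Not stated | Not stated |
| Masking to visit or date | Not stated | Not stated | Not stated |
| Reading order of the pair | Not stated | Not stated | Not stated |
| Cut-off for the three categories | Not stated | Not stated | Not stated |

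A labelled, in-order read satisfies every cell. So does a masked read that is decoded afterwards. The plan permits both and requires neither.

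**3. Is the open element exposed to expectation?** Section 2.1 gives the direction expected for levator bulk. The design has no untreated pairs. Section 10 uses MRI in judging response. All three conditions are in the documents.

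**4. What would a reader shift do to the planned test?** The size of any shift is an assumption. This step shows sensitivity only.

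- Inputs: n = 30 pairs (Section 10); two-sided 0.05 (assumed, since no level is stated); no true change; normally distributed changes; a constant reader shift of b SDs of the change.
- Signed-rank statistic W has maximum 30 × 31 / 2 = 465. The exact lower critical value is 137, so the test rejects if W ≤ 137 or W ≥ 465 − 137 = 328. The exact size is 0.0497.
- Simulated rejection rates (40,000 trials each):

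| Assumed shift b | Rejection rate |
|---|---|
| 0 | 0.049 |
| 0.2 | 0.18 |
| 0.3 | 0.35 |
| 0.4 | 0.55 |
| 0.5 | 0.74 |

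These rates concern the quantitative measurements. They do not carry over to the three-category call, which the plan does not test. Masking does not change the number of subjects needed.

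**The case against.** The strongest reply is that the plan is silent rather than wrong. A reader might infer from Section 10.1 that the scans will be compared with their order known. The sentence does not say so. It fixes the direction in which change is reported, and the result of a masked read decoded later would be written in the same words. This stands: the point is what the plan fails to require, not what it prescribes.

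A reader might also take the category call to be the whole MRI endpoint. It is not. The endpoint is quantitative and separately tested, and the call is a descriptive supplement. That limits the weight of the call but does not remove the concern, because masking is not stated for the measurements either.

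Nor does the plan make MRI its most objective outcome. It does not rank its secondary endpoints, and 24-hour pad weight and maximum urethral closure pressure are also instrument-based.

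Two further limits hold. The anticipated growth concerns levator bulk, while the parameters named in Section 3.3 are dimensions of the hiatus, for which no direction is given. And a reading rule could exist in the Roles and Responsibilities pages, which I did not have, in the standard operating procedures mentioned in Section 11, or in the Manual of Procedures mentioned in Section 13.5. If so, the protocol need only cite it.

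**Conclusion.** The concern holds as an omission. Sections 3.3, 8 and 10.1 do not require masking to scan order and give no cut-off for the three categories, so a labelled read would comply. In an open-label, single-arm study that anticipates levator growth and counts MRI towards response, both the tested measurements and the descriptive call are open to expectation bias.

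Its size cannot be estimated from the documents. The rejection rates above depend on assumed shifts and on an assumed two-sided 5% level, and should not be read as a forecast. MRI is one of 12 secondary endpoints in an unpowered feasibility study, and the primary endpoint is unaffected. This is a cheap improvement and not a flaw that undermines the trial.

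**What to change.** State in Sections 8 and 10.1 that:

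- all pelvic-floor muscle measurements and the three-category call are read in one batch after the last Week 12 scan;
- dates and visit labels are removed, and each subject's two scans are presented in random order as scan A and scan B;
- the reads are locked before A and B are decoded to Baseline and Week 12;
- both endometrial thickness reads (baseline for eligibility, end of treatment for safety) stay unmasked and on time, separate from the muscle read.

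Masking does not supply a category cut-off. The rule for calling no change should be written down before the batch read starts. The documents give no measurement-error figure from which I could propose a value.

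**Cost.** Label removal and a random-order list; the same scans and the same reader can be used, with no change in sample size, visits or burden on subjects. The downside is that muscle results are available only at the end of the study. If one person does both the endometrial and the muscle reads, that person will have seen the images labelled. The delay and random order reduce recall but do not exclude it.
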